3. PATIENT SELECTION

3.1 Eligibility Criteria

- 3.1.1 Patients must have documented *EWSR1/ATF1* or *EWSR1/CREB1* translocation or histologically confirmed clear cell sarcoma, documented grade 2 or 3 conventional chondrosarcoma, or documented dedifferentiated chondrosarcoma. The disease must not be curable by surgery.
- 3.1.2 Patients must have measurable disease, defined as at least one lesion that can be accurately measured in at least one dimension (longest diameter to be recorded for non-nodal lesions and short axis for nodal lesions) as ≥ 20 mm (≥ 2 cm) by chest x-ray or as ≥ 10 mm (≥ 1 cm) with CT scan, MRI, or calipers by clinical exam. See Section [11](#) (Measurement of Effect) for the evaluation of measurable disease.
- 3.1.3 Patients with newly diagnosed, unresectable, metastatic and measurable clear cell sarcoma, *EWSR1/ATF1* or *EWSR1/CREB1* translocation, grade 2 or 3 conventional chondrosarcoma, or dedifferentiated chondrosarcoma will also be eligible if they show clinical evidence of disease progression (including history and increasing physical symptoms). On-study documentation will include a physician’s rationale that supports

evidence of clinical disease progression (i.e., increasing tumor pain).

3.1.4 Age ≥ 2 years at the NCI Clinical Center (≥ 12 years at other participating sites)

3.1.5 ECOG performance status ≤ 2 (Karnofsky or Lansky $\geq 70\%$, see [Appendix A](#)).

3.1.6 Life expectancy of greater than 3 months.

3.1.7 Patients must have adequate organ and marrow function as defined below:

- absolute neutrophil count $\geq 1,000/\text{mcL}$
- platelets $\geq 100,000/\text{mcL}$
- hemoglobin $\geq 8 \text{ g/dL}$
- total bilirubin \leq institutional upper limit of normal (ULN)
(however, patients with known Gilbert disease who have serum bilirubin level $\leq 3 \times \text{ULN}$ may be enrolled)
- AST(SGOT)/ALT(SGPT) $\leq 3 \times$ institutional ULN
(AST and/or ALT $\leq 5 \times \text{ULN}$ for patients with liver involvement)
- alkaline phosphatase $\leq 2.5 \times \text{ULN}$
($\leq 5 \times \text{ULN}$ for patients with documented liver involvement or bone metastases)
- creatinine
For adult patients (≥ 18 years of age):
 $\geq 30 \text{ mL/min/1.73 m}^2$ by Cockcroft-Gault

$\frac{(140 - \text{age}) \times (\text{weight in kg})}{72 \times (\text{serum creatinine in mg/dL})} \quad (\times 0.85 \text{ if female})$
--

For pediatric patients (< 18 years of age), a serum creatinine based on age and gender as follows:

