11.2 RECIST Response Assessment

11.2.1 Definitions

Evaluable for Toxicity. All patients will be evaluable for toxicity from the time of their first treatment with atezolizumab.

Evaluable for Objective Response Rate. Only those patients who have measurable disease present at baseline and have received at least one dose of therapy will be considered evaluable for the primary endpoint of objective response rate. These patients will have their response classified according to the definitions stated below. (Note: Patients who exhibit objective disease progression prior to the end of Cycle 1 will also be considered evaluable.)

Evaluable Non-Target Disease Response. Patients who have lesions present at baseline that are evaluable but do not meet the definitions of measurable disease, have received at least one cycle of therapy, and have had their disease re-evaluated will be considered evaluable for non-target disease. The response assessment is based on the presence, absence, or unequivocal progression of the lesions.

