11.2.2 Disease Parameters

Measurable Disease. Measurable lesions are defined as those that can be accurately measured in at least one dimension (longest diameter to be recorded) as ≥ 20 mm (≥ 2 cm) by chest x-ray or as ≥ 10 mm (≥ 1 cm) with CT scan, MRI, or calipers by clinical exam. All tumor measurements must be recorded in millimeters (or decimal fractions of centimeters).

Malignant Lymph Nodes. To be considered pathologically enlarged and measurable, a lymph node must be ≥ 15 mm (≥ 1.5 cm) in short axis when assessed by CT scan (CT scan slice thickness recommended to be no greater than 5 mm [0.5 cm]). At baseline and in follow-up, only the short axis will be measured and followed.

Non-Measurable Disease. All other lesions (or sites of disease), including small lesions (longest diameter < 10 mm [< 1 cm] or pathological lymph nodes with ≥ 10 to < 15 mm [≥ 1 to < 1.5 cm] short axis), are considered non-measurable disease. Bone lesions, leptomeningeal disease, ascites, pleural/pericardial effusions, lymphangitis cutis/pulmonitis, inflammatory breast disease, and abdominal masses (not followed by CT or MRI), are considered as non-measurable.

Note: Cystic lesions that meet the criteria for radiographically defined simple cysts should not be considered as malignant lesions (neither measurable nor non-measurable) since they are, by definition, simple cysts.

‘Cystic lesions’ thought to represent cystic metastases can be considered as measurable lesions, if they meet the definition of measurability described above. However, if non-cystic lesions are

present in the same patient, these are preferred for selection as target lesions.

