Target Lesions. All measurable lesions up to a maximum of 2 lesions per organ and 5 lesions in total, representative of all involved organs, should be identified as **target lesions** and recorded and measured at baseline. Target lesions should be selected on the basis of their size (lesions with the longest diameter), be representative of all involved organs, but in addition should be those that lend themselves to reproducible repeated measurements. It may be the case that, on occasion, the largest lesion does not lend itself to reproducible measurement in which circumstance the next largest lesion which can be measured reproducibly should be selected. A sum of the diameters (longest for non-nodal lesions, short axis for nodal lesions) for all target lesions will be calculated and reported as the baseline sum diameters. If lymph nodes are to be included in the sum, then only the short axis is added into the sum. The baseline sum diameters will be used as reference to further characterize any objective tumor regression in the measurable dimension of the disease.

Non-Target Lesions. All other lesions (or sites of disease) including any measurable lesions over and above the 5 target lesions should be identified as **non-target lesions** and should also be recorded at baseline. Measurements of these lesions are not required, but the presence, absence, or in rare cases unequivocal progression of each should be noted throughout follow-up.

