 - Increase in size of previously identified new lesion(s) (an increase of at least 5 mm in the absolute value of the sum of those considered to be target new lesions) or additional new lesions.
- RECIST 1.1 criteria are met in lesions types (target or non-target or new lesions) where progression was not previously identified, including the appearance of additional new lesions.

If iUPD is not confirmed at the next assessment, then the appropriate response will be assigned (iUPD if the criteria are still met, but no worsening, or iSD, iPR, or iCR if those criteria are met compared to baseline). The prior documentation of iUPD does not preclude assigning iCR, iPR,

or iSD in subsequent time-point assessments or as best overall response (BOR) providing that iCPD is not documented at the next assessment after iUPD (*Lancet Oncol* 18:e143-e152, 2017 - Table 2).

New lesions:

New lesions should be assessed and measured as they appear using RECIST 1.1 criteria (maximum of 5 lesions, no more than 2 per site, at least 10 mm in long axis [or 15 mm in short axis for nodal lesions]), and recorded as New Lesions - Target (NLT) and New Lesion - Non-Target (NLNT) to allow clear differentiation from baseline target and non-target lesions.

New lesions may either meet the criteria of NLT or NLNT to drive iUPD (or iCPD). However, the measurements of target lesions should NOT be included in the sum of measures of original target lesions identified at baseline. Rather, these measurements will be collected on a separate table in the case record form.

PD is confirmed in the New Lesion category if the next imaging assessment, conducted at least 4 weeks (but not more than 8 weeks) after iUPD confirms further progression from iUPD with either an increase of at least 5 mm in the absolute value of the sum of NLT OR an increase (but not necessarily unequivocal increase) in the size of NLNT lesions OR the appearance of additional new lesions.

Time-point (TP) iResponse

Target Lesions*	Non-Target Lesions*	New Lesions*	Time Point Response	
			No prior iUPD**	Prior iUPD**, ***
iCR	iCR	No	iCR	iCR
iCR	Non-iCR/Non-iUPD	No	iPR	iPR
iPR	Non-iCR/Non-iUPD	No	iPR	iPR
iSD	Non-iCR/Non-iUPD	No	iSD	iSD
iUPD with no change OR decrease from last TP	iUPD with no change OR decrease from last TP	Yes	NA	NLs confirms iCPD if NLs were previously identified and increase in size (≥ 5 mm in SOM for NLT or any increase for NLNT) or number. If no change in NLs (size or number) from last TP, remains iUPD.

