13. STATISTICAL CONSIDERATIONS

13.1 Study Design/Endpoints

This study will enroll adult and pediatric patients, but only adults will be included in the primary and interim analyses. For adult patients, a Simon two stage design will be employed within each of the three study cohorts, with a maximum of 17 evaluable patients per cohort. For each cohort, accrual will be halted at 9 patients to evaluate for response before further enrollment. If within 9

months of the ninth patient being enrolled to a cohort no responses are observed among the initial 9 patients in that cohort, the cohort will be terminated early and declared negative; if at least one response is observed, accrual to that cohort will continue. If at least 3 responses (at least 17.6%) are observed among the initial 17 evaluable patients in a disease cohort, this regimen will be considered worthy of further testing in that disease. This design yields at least 81% power to detect a true response rate of at least 25% in each cohort. It yields at least .95 probability of a negative result if the true response rate in each cohort is no more than 5%, with at least .63 probability of early negative stopping for each cohort. Per the RECIST v 1.1 guidelines ([Section 13.4.2](#)), all eligible patients who are treated on study will be included in the primary and interim response analyses.

The trial will remain open to pediatric patients with CCS and CS for as long the study is accruing, up to a maximum of 8 pediatric patients across the three study histologies. These patients will not provide research biopsies, but will have the opportunity to be treated due to the possibility of therapeutic benefit. Within each cohort, a maximum of 2 pediatric patients will be enrolled prior to the completion of the first-stage futility analysis. If none of the initial 9 adult patients enrolled to a cohort respond within 9 months of the ninth adult patient being enrolled, no additional adult or pediatric patients with that histology will be enrolled. If accrual of adult patients proceeds to the second stage within a cohort, additional pediatric patients with that histology may be enrolled until the 17th adult patient is enrolled (as long as the limit of 8 total pediatric patients across all cohorts has not been reached), at which point all accrual of patients with this histology will be halted.

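### Section 3.1.2 accepts a 10 mm short-axis lymph node as measurable disease, but Section 11.2.2 requires 15 mm, so a patient with only small nodes can be eligible and counted yet have no target lesion

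*Combined protocol and SAP*

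**What the plan says.** **Eligibility (Section 3.1.2).** Measurable disease is at least one lesion, with the dimension given as "longest diameter to be recorded for non-nodal lesions and short axis for nodal lesions". The size threshold is 20 mm by chest x-ray, or 10 mm "with CT scan, MRI, or calipers by clinical exam. See Section" 11. There is no separate threshold for nodes.

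**Response assessment (Section 11.2.2).** "To be considered pathologically enlarged and measurable, a lymph node must be" at least 15 mm in short axis on CT. Smaller lesions, including nodes of 10 to under 15 mm short axis, "are considered non-measurable disease". Target lesions come only from measurable disease: "All measurable lesions up to a maximum of 2 lesions per organ and 5 lesions in total". The iRECIST rules in Section 11.3 use the same nodal size for new lesions: "15 mm in short axis for nodal lesions".

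**Who is counted.** Section 11.2.1 limits evaluability for response rate: "Only those patients who have measurable disease present at baseline and have received at least one dose of therapy". Section 13.1 says that "all eligible patients who are treated on study will be included in the primary and interim response analyses", and Section 13.4.2 likewise bases the main response analysis and all conclusions on eligible patients.

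**The concern.** Followed as written, Section 3.1.2 admits an adult whose only disease is a node of, say, 12 mm short axis on CT. Section 11 then gives that patient no target lesion, so a partial response cannot be scored from target-lesion measurements. Section 11.2.1 removes the patient from the response-rate set, while Sections 13.1 and 13.4.2 keep the patient in.

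The error could also run the other way. Section 11.2.4.2 needs only that nodes fall below 10 mm short axis for a non-target complete response, and Section 11.2.4.3 allows an overall complete response in patients with non-target disease only. A node measured at 10 or 11 mm could cross that line with a change of a millimetre or two.

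Each cohort stops on 0 responses in 9 adults and is declared positive on 3 in 17, so one misclassified patient can affect the decision.

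**Working it through.** **Inputs (Section 13.1).** Per cohort: 9 patients in stage 1, stop if 0 respond; 8 more in stage 2; positive if at least 3 of 17 respond. The uninteresting rate is 5% and the target rate 25%. X1 and X2 are the responses in stages 1 and 2.

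**Formula.**
P(early stop) = (1 − p)^9
P(positive) = P(X1=1)·P(X2≥2) + P(X1=2)·P(X2≥1) + P(X1≥3)

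**The plan's own figures, p = 0.25.**
- P(X1=0) = 0.75^9 = 0.0751; P(X1=1) = 0.2253; P(X1=2) = 0.3003; P(X1≥3) = 0.3993
- With 8 in stage 2: P(X2≥2) = 0.6329; P(X2≥1) = 0.8999
- Power = 0.2253×0.6329 + 0.3003×0.8999 + 0.3993 = 0.812 (stated: at least 81%)

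**At p = 0.05.** The same formula gives P(positive) = 0.0466, so P(negative) = 0.953 (stated: at least .95). Early stopping is 0.95^9 = 0.630 (stated: at least .63). All three stated figures reproduce.

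**Bound A: a counted patient who cannot respond.** The number of such patients is an assumption, and the denominator is that of Sections 13.1 and 13.4.2. Remove the patient from the relevant binomial and keep the rule at 3 responses.
- One in stage 1 (8 can respond): P(X1=1) = 0.2670, P(X1=2) = 0.3115, P(X1≥3) = 0.3215. Power = 0.2670×0.6329 + 0.3115×0.8999 + 0.3215 = 0.771. Stopping at a true 25% rises from 7.5% to 0.75^8 = 10.0%.
- One in stage 2 (7 can respond): P(X2≥2) = 0.5551, P(X2≥1) = 0.8665. Power = 0.2253×0.5551 + 0.3003×0.8665 + 0.3993 = 0.785. Early stopping is unchanged.
- One in each stage: 0.740. Two in stage 1: 0.721.

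**Bound B: a counted patient who is certain to be scored as a complete response, p = 0.05.** If this patient is in stage 1, the futility stop cannot occur and the cohort is positive if at least 2 of the other 16 respond:
1 − 0.95^16 − 16×0.05×0.95^15 = 1 − 0.4401 − 0.3706 = 0.189, against 0.047 as planned.

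Bound B is an extreme. Section 11.1 asks for a confirmatory scan at least 4 weeks after a response, so a chance change of a millimetre would have to persist.

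**The case against.** **The cross-reference.** Section 3.1.2 sends the reader to Section 11, and both Sections 11.2.2 and 11.3 use 15 mm for nodes. So 15 mm is very probably what was meant. That stands as to intent. But the pointer does not say that Section 11 overrides the stated 10 mm, and a screener who sees nodes mentioned in Section 3.1.2 has no reason to look for another cutoff.

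**Palpable nodes.** Section 11.2.3 treats superficial lesions, palpable nodes included, as measurable from 10 mm by calipers. Some small nodes therefore have a route to measurability inside Section 11. This stands: the mismatch concerns nodes assessed on imaging, and a bare 15 mm rule would leave Section 11.2.3 in conflict.

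**The denominator.** The success rule in Section 13.1 refers to 17 evaluable patients, and Section 13.2 allows for some who are not evaluable: 68 − 3×17 = 17 spare places, or 17 − 8 = 9 if the 8 pediatric patients are additional. If Section 11.2.1 governs, a node-only patient would be replaced by the final analysis and the stage-2 loss would not arise. This also stands. The bounds above depend on Sections 13.1 and 13.4.2 governing.

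**Frequency.** A reader might infer a rate from the clear cell sarcoma series in Section 2.1, where 19 of 52 patients developed regional nodal metastasis. The documents do not support that. Those cases arose over follow-up; 2 patients presented with regional nodal disease, and 30 developed distant metastasis, 27 of them pulmonary. No figure is given for incurable disease confined to nodes of 10 to under 15 mm, and the chondrosarcoma background describes no nodal spread.

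**Conclusion.** The contradiction between Sections 3.1.2 and 11.2.2 is real and reaches the primary endpoint. Its effect is uncertain and probably small, because it needs patients whose only disease is small nodes on imaging.

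Three stronger conclusions are tempting and do not follow:

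- **That the trial has less power than stated.** The plan's operating characteristics are correct for its rule. The values 0.771 and 0.785 are what one assumed non-responding patient would cost in a cohort.
- **That response rates are biased downward.** Zero response is one extreme; a near-automatic complete response is the other, taking the chance of a positive result at a true 5% from 4.7% to about 18.9% if it falls in stage 1.
- **That correcting the nodal threshold makes the eligible and response-evaluable sets the same.** Section 11.2.2 also makes bone lesions non-measurable, and Section 11.2.3 sets the minimum size at twice the slice thickness when CT slices exceed 5 mm. Section 3.1.2 states neither. With two chondrosarcoma cohorts, the bone-lesion rule may matter at least as much.

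The textual conflict is certain. The numerical effect is illustrative. The correction is worth making because it is cheap and the decision in each cohort rests on few responses.

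**What to change.** 1. In Section 3.1.2 and the eligibility checklist, state that measurability for eligibility is as defined in Sections 11.2.2 and 11.2.3: nodes assessed by CT at least 15 mm short axis; non-nodal lesions at least 10 mm longest diameter by CT or MRI, or 20 mm by chest x-ray; the bone-lesion and slice-thickness rules also apply.
2. Reconcile the 10 mm caliper rule for palpable nodes in Section 11.2.3 with the nodal rule in Section 11.2.2.
3. Align Section 11.2.1 with Sections 13.1 and 13.4.2, so that one denominator governs both the 9-patient and the 17-patient decision.

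The cost is a short amendment to the text and the checklist. A few patients with only small nodal disease would not be enrolled. Sample size and decision rule do not change, and if every counted patient has a target lesion, power stays at 0.812 and the chance of a positive result at a 5% rate stays at 0.047.

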3.2 Exclusion Criteria

- 3.2.1 Any prior therapy must have been completed ≥ 4 weeks or, if known, ≥ 5 half-lives of the prior agent (whichever is shorter) prior to enrollment on protocol (minimum of 1 week between prior therapy and study enrollment), and the participant must have recovered to eligibility levels from prior toxicity. Patients should be at least 6 weeks out from nitrosoureas and mitomycin C. Prior definitive radiation should have been completed ≥ 4 weeks or palliative radiation should have been completed ≥ 2 weeks prior to study enrollment and all associated toxicities resolved to eligibility levels (patients on study may be eligible for palliative radiotherapy to non-targeted lesions after 2 cycles of therapy at the PI's discretion). Patients who have had prior monoclonal antibody therapy must have completed that therapy ≥ 6 weeks (or 3 half-lives of the antibody, whichever is shorter) prior to enrollment on protocol (minimum of 1 week between prior therapy and study enrollment). A patient who has received a cumulative dose of >350 mg/m² of anthracycline (regardless of cardioprotectant) may only be enrolled if their

ejection fraction measured by an echocardiogram is within normal institutional limits.

- 3.2.2 Prior treatment with anti-PD-1, or anti-PD-L1 therapeutic antibody or pathway-targeting agents.
- Patients who have received prior treatment with anti-CTLA-4 may be enrolled, provided the following requirements are met:
 - Minimum of 12 weeks from the first dose of anti-CTLA-4 and >6 weeks from the last dose
 - No history of severe immune-related adverse effects from anti-CTLA-4 (NCI CTCAE Grade 3 and 4)
- 3.2.3 Treatment with any other investigational agent within 4 weeks (or within five half-lives of the investigational product, whichever is shorter) prior to Cycle 1, Day 1 (minimum of 1 week between prior therapy and study enrollment). Patients must be ≥ 2 weeks since any investigational agent administered as part of a Phase 0 study (also referred to as an “early Phase I study” or “pre-Phase I study” where a sub-therapeutic dose of drug is administered) at the Coordinating Center PI’s discretion, and should have recovered to eligibility levels from any toxicities.
- 3.2.4 Treatment with systemic immunostimulatory agents (including, but not limited to, interferon- α or interleukin-2 [aldesleukin]) within 6 weeks prior to Cycle 1, Day 1.
- 3.2.5 Treatment with systemic immunosuppressive medications (including, but not limited to, prednisone [>10 mg/day], cyclophosphamide, azathioprine, methotrexate, thalidomide, and anti-tumor necrosis factor [anti-TNF] agents) within 2 weeks prior to Cycle 1, Day 1.
- Patients who have received acute, low dose, systemic immunosuppressant medications (e.g., a one-time dose of dexamethasone for nausea) may be enrolled.
 - The use of inhaled corticosteroids and systemic mineralocorticoids (e.g., fludrocortisone) for patients with orthostatic hypotension or adrenocortical insufficiency is allowed.
- 3.2.6 Patients taking bisphosphonate therapy for symptomatic hypercalcemia. Use of bisphosphonate therapy for other reasons (e.g., bone metastasis or osteoporosis) is allowed.
- 3.2.7 Known hypersensitivity to Chinese hamster ovary cell products or other recombinant human antibodies.
- 3.2.8 History of severe allergic, anaphylactic, or other hypersensitivity reactions to chimeric or humanized antibodies (i.e., antibodies with generic names ending in “ximab” or “zumab”, respectively) or fusion proteins
- 3.2.9 Uncontrolled intercurrent illness including, but not limited to, ongoing or active infection, symptomatic congestive heart failure, unstable angina pectoris, cardiac

arrhythmia, or psychiatric illness/social situations that would limit compliance with study requirements.

- 3.2.10 Pregnant women are excluded from this study because atezolizumab is an investigational agent with the unknown potential for teratogenic or abortifacient effects. Because there is an unknown but potential risk for adverse events in nursing infants secondary to treatment of the mother with atezolizumab, breastfeeding should be discontinued if the mother is treated with atezolizumab.
- 3.2.11 Patients with a history of HIV-positive on antiretroviral therapy are eligible with an undetectable viral load. For these patients, an HIV viral load test must be completed within 28 days prior to enrollment.
- 3.2.12 Known clinically significant liver disease, including active viral, alcoholic, or other hepatitis; cirrhosis; fatty liver; and inherited liver disease.
- Patients with past or resolved hepatitis B infection (defined as having a negative hepatitis B surface antigen [HBsAg] test and a positive anti-HBc [antibody to hepatitis B core antigen] antibody test) are eligible. For these patients, HBsAg and anti-HBc tests must be done within 28 days prior to enrollment.
 - Patients positive for hepatitis C virus (HCV) antibody are eligible only if polymerase chain reaction (PCR) is negative for HCV RNA. For these patients, an HCV RNA test must be done within 28 days prior to enrollment.
- 3.2.13 History or risk of autoimmune disease, including, but not limited to, systemic lupus erythematosus, rheumatoid arthritis, inflammatory bowel disease, vascular thrombosis associated with antiphospholipid syndrome, Wegener's granulomatosis, Sjögren's syndrome, Bell's palsy, Guillain-Barré syndrome, multiple sclerosis, autoimmune thyroid disease, vasculitis, or glomerulonephritis.
- Patients with a history of autoimmune hypothyroidism on a stable dose of thyroid replacement hormone may be eligible.
 - Patients with autoimmune hyperthyroid disease not requiring immunosuppressive treatment may be eligible.
 - Patients with controlled Type 1 diabetes mellitus on a stable insulin regimen may be eligible.
 - Patients with eczema, psoriasis, lichen simplex chronicus, or vitiligo with dermatologic manifestations only (e.g., patients with psoriatic arthritis would be excluded) are permitted provided that they meet the following conditions:
 - Patients with psoriasis must have a baseline ophthalmologic exam to rule out ocular manifestations
 - Rash must cover less than 10% of body surface area (BSA)
 - Disease is well controlled at baseline and only requiring low potency topical steroids (e.g., hydrocortisone 2.5%, hydrocortisone butyrate 0.1%, flucinolone 0.01%, desonide 0.05%, aclometasone dipropionate 0.05%)
 - No acute exacerbations of underlying condition within the last 12 months (not requiring psoralen plus ultraviolet A radiation [PUVA], methotrexate, retinoids, biologic agents, oral calcineurin inhibitors; high potency or oral

steroids)

- 3.2.14 History of idiopathic pulmonary fibrosis, pneumonitis (including drug induced), organizing pneumonia (i.e., bronchiolitis obliterans, cryptogenic organizing pneumonia, etc.), or evidence of active pneumonitis on screening chest computed tomography (CT) scan. History of radiation pneumonitis in the radiation field (fibrosis) is permitted.
- 3.2.15 Patients with active tuberculosis (TB) are excluded.
- 3.2.16 Severe infections within 4 weeks prior to Cycle 1, Day 1, including, but not limited to, hospitalization for complications of infection, bacteremia, or severe pneumonia.
- 3.2.17 Signs or symptoms of infection within 2 weeks prior to Cycle 1, Day 1.
- 3.2.18 Received oral or intravenous (IV) antibiotics within 2 weeks prior to Cycle 1, Day 1. Patients receiving prophylactic antibiotics (e.g., for prevention of a urinary tract infection or chronic obstructive pulmonary disease) are eligible.
- 3.2.19 Major surgical procedure within 28 days prior to Cycle 1, Day 1 or anticipation of need for a major surgical procedure during the course of the study.
- 3.2.20 Administration of a live, attenuated vaccine within 4 weeks before Cycle 1, Day 1 or anticipation that such a live, attenuated vaccine will be required during the study and up to 5 months after the last dose of atezolizumab.
 - Influenza vaccination should be given during influenza season only (approximately October to March). Patients must not receive live, attenuated influenza vaccine within 4 weeks prior to Cycle 1, Day 1 or at any time during the study.

